The required analysis (e.g. ANCOVA) is then performed separately within each imputation dataset (as identified by variable *_imputation_*). To obtain the final result of the imputation process the analysis result from each imputation dataset needs to be combined according to Rubin’s rule as outlined below:

```
ods output parameterestimates=mi_result;  
proc mianalyze data=;  
modeleffects estimate;  
stderr estimate_se;  
run;
```

The *estimate* and *estimate_se* parameters come from the analysis model used to analyze the imputed variable within each imputation dataset (e.g., from the lsmean estimate of the treatment difference and its standard error obtained from PROC LOGISTIC or PROC MIXED)

To obtain binary response rates and confidence intervals for individual treatment groups the following process should be followed (exemplified for one visit):

```
ods output binomialprop=bin_est;  
proc freq data=;  
by treatment_imputation_;
```

```
table response / binomial (cl=wilson correct);  
run;
```

Then apply a logit transformation on the saved proportions and derive its standard error:

```
data bin_est; set bin_est;  
estimate=log(_bin_/(1-_bin_));  
estimate_se=e_bin/(_bin_*(1-_bin_));  
run;
```

[figure not shown]
The transformed binomial proportion estimates and its standard errors are then combined by applying Rubin's rules (Rubin, 1987) as described above using PROC MIANALYZE. Before presenting the combined data it needs to be transformed back as follows:

[figure not shown]
```
data mi_result; set mi_result;  
prop_est=1/(1+exp(-estimate));  
prop_lower=1/(1+exp(-lclmean));  
prop_upper=1/(1+exp(-uclmean));  
run;
```

If all responses are imputed the same as 0 (or 1) for all imputation datasets for a specific treatment or subgroup then the between-imputation-variation will be zero. The combined final response rate for the specific treatment or subgroup would be presented as seen in any of the imputed datasets together with 95% CI from Wilson's method (as obtained from PROC FREQ).

The following steps will be performed to handle special cases:

- If after imputation all responses (observed+imputed) are the same either 0 or 1 for all imputation datasets for a specific treatment or subgroup it will not be possible to perform a logit transformation and the response rate (0% or 100%) for these cases will be presented together with the 95% CI

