5.5.1.4 Analysis of binary and categorical data

5.5.1.4.1 Summary statistics for binary and categorical data

Summary statistics for discrete variables will be presented in contingency tables and will include count and frequency in each category. If applicable, confidence intervals will be derived as well based on the score method including continuity correction ([Newcombe 1998](#)):

With z as $(1-\alpha/2)$ -quantile of the standard normal distribution (SAS: $z=\text{probit}(1-\alpha/2)$), n as total number of subjects (i.e. number of subjects in the denominator), p as estimated crude incidence (number of subjects with event / n) and $q=1-p$)

Then the lower limit is

$$L = 100 \times \max \left(0, \frac{2np + z^2 - 1 - z \sqrt{z^2 - 2 - \frac{1}{n} + 4p(nq + 1)}}{2(n + z^2)} \right)$$

And the upper limit is

$$U = 100 \times \min \left(0, \frac{2np + z^2 + 1 + z \sqrt{z^2 + 2 - \frac{1}{n} + 4p(nq - 1)}}{2(n + z^2)} \right)$$

In addition, if $L > p$ then $L = p$ and if $U < p$ then $U = p$.

The placebo-adjusted response rates include 95% confidence interval will be derived using PROC FREQ with RISKDIFF statement. Note the response value should be sorted with '1' ahead of '0'. Fisher's exact test will be applied to rate events, pairwise treatment group comparisons to placebo to active controls (using PROC PREQ with FISHER statement). If appropriate, an exact $100*(1-\alpha)\%$ confidence interval (Clopper-Pearson 1934) will be obtained by using the SAS procedure PROC FREQ with the EXACT BINOMIAL statement. However, the confidence interval derived via the score method including continuity correction will be the default in safety analysis.

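### The per-arm step after multiple imputation names no response level; run as printed, it would give each arm's non-response rate

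*SAP*

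**What the plan says.** SAP 5.5.1.2.1 introduces the step with "To obtain binary response rates and confidence intervals for individual treatment groups the following process should be followed". For each treatment and imputation it saves the binomial table ("ods output binomialprop=bin_est") from the statement "table response / binomial (cl=wilson correct" plus the closing bracket. The block prints no level, ordering option, format or recode for the response.

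The saved proportion goes through a logit ("estimate=log(_bin_/(1-_bin" and closing brackets), is pooled by Rubin's rules, and is returned to the proportion scale ("prop_est=1/(1+exp(-estimate" and closing brackets).

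Three other places bear on the coding:
- The special-case text in the same section treats responses as 0 or 1: "If all responses are imputed the same as 0 (or 1) for all imputation datasets".
- The primary-model code in SAP 5.5.1.1 names 1 as the event.
- SAP 5.5.1.4.1, for its own PROC FREQ risk difference, says: "Note the response value should be sorted with '1' ahead of '0" (closing quote mark omitted). That instruction is not repeated in the multiple-imputation block.

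Protocol 12.4.4 lists multiple imputation among the ways in which the effect of missing ASAS40 data may be examined. The SAP's document history says that the sensitivity analyses were moved to supportive analyses.

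**The concern.** The block is meant to deliver response rates, but it leaves the choice of level to the software. With 0/1 coding and levels taken in ascending order, the first level is 0, which is non-response. The SAP fixes the level for the primary model and gives an ordering instruction for the risk difference, so its authors knew that this matters. The safeguard is missing here.

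At stake is a supportive table in which placebo appears to do better than secukinumab while the primary table shows the reverse. The Week 16 analysis is for regulatory submission (SAP 2.14), so such a table would at least prompt queries.

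**Working it through.** **The plan's own figures.** The SAP prints no figure for this output. Its planning rates are used below. The probabilities of success built on them (SAP 3.1, Scenario 2: 77.3% and 90.7%) reproduce by exact binomial enumeration with 60 per arm (0.7730 and 0.9072), but they do not bear on this point.

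**Inputs**
- Planning ASAS40 rates in TNF-naive participants: secukinumab 0.415, placebo 0.292 (SAP 3.1).
- 120 TNF-naive participants at 1:1, so 60 per arm (SAP 3.1).
- 100 imputations (SAP 5.5.1.2.1).
- Response coded 0/1, with 1 = responder (SAP 5.5.1.1, 5.5.1.2.1 and 5.5.1.4.1).
- Assumption from outside the documents: without a named level, the BINOMIAL option reports the first level of the table, and without an ordering option, levels are in ascending value order.

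**Step 1: what is saved.** Let p be an arm's response proportion in one imputed dataset. Under the assumption, the saved proportion is 1 − p.

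**Step 2: logit.** logit(1 − p) = −logit(p). The standard error on this scale is the binomial standard error divided by p(1 − p), which is the same for p and 1 − p.

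**Step 3: pooling.** If the pooled logit for responders is Q with total variance T, the pooled logit for non-responders is −Q. The within- and between-imputation variances do not change, so T does not change either.

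**Step 4: back-transform.** 1/(1 + exp(Q)) = 1 − 1/(1 + exp(−Q)). The chain therefore returns one minus the pooled response rate, with limits (1 − upper, 1 − lower). No step reverses this.

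**Step 5: size at the planning rates**
- Secukinumab: 1 − 0.415 = 0.585.
- Placebo: 1 − 0.292 = 0.708.
- Displayed gap: 0.585 − 0.708 = −0.123, against a true gap of 0.415 − 0.292 = +0.123.

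**Step 6: numerical check with the printed formulas.** This assumes 6 of 60 missing per arm, imputed at the planning rates, with 22 of 54 observed responders on secukinumab and 16 of 54 on placebo.

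| Arm | Level 1 named | As printed (level 0) |
|---|---|---|
| Secukinumab | 0.4105 (0.2882 to 0.5450) | 0.5895 (0.4550 to 0.7118) |
| Placebo | 0.2940 (0.1889 to 0.4269) | 0.7060 (0.5731 to 0.8111) |

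Each entry on the right is one minus its counterpart on the left, with the limits exchanged.

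**Range.** If the software took level 1 by default, or the data were recoded first, the output would be 41.5% and 29.2%. Otherwise it is 58.5% and 70.8%.

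**The case against.** The code is a template. The SAP says that covariates and visits can be added or removed, and the input dataset names are blank. The stated purpose is response rates, so a competent programmer may well supply the level. That stands, and it limits the claim to what the code would give if run as printed. It does not remove the point, because no correction is printed and the SAP tells the programmer to follow this process.

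The default level is a property of the software and is not stated in the documents. That also stands. The ordering instruction in SAP 5.5.1.4.1 supports it only indirectly.

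The error would be easy to see. Multiple imputation can raise an arm's rate above the non-responder-imputation rate by at most the share of the arm that had been set to non-response by rule. A placebo rate moving from 29.2% to 70.8% is a rise of 41.6 points, which needs at least 41.6% of the arm to have been so classified. This is a good reason to rank the point low.

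The public text does not include the SAP's supportive-analysis section (2.5.4), and Protocol 12.4.4 only says that multiple imputation may be used. Whether and where per-arm ASAS40 rates from this step are tabulated cannot be seen.

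A reader might infer that the treatment effect itself would be reversed. The documents do not support that. The primary analysis uses non-responder imputation (SAP 2.5.3) and models the event coded 1 (SAP 5.5.1.1). The pooled contrast uses an estimate and standard error from the analysis model (SAP 5.5.1.2.1). No printed step subtracts the two per-arm rates, so the −12.3 points above is what a reader of the table would compute, not a planned output.

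A reader might also see a material gap in the special-case rules when some, but not all, imputed datasets have a 0% rate. For ASAS40 the case is negligible: with 60 per arm at the placebo planning rate, the chance of no responder is 0.708^60, about 1 in 10^9.

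**Conclusion.** The point holds, as a minor one. Run as printed, the per-arm step in SAP 5.5.1.2.1 would report the non-response rate of each arm under the name of a response rate: 58.5% and 70.8% in place of 41.5% and 29.2% at the planning rates, with the confidence limits mirrored in the same way.

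This rests on three things: the SAP's 0/1 coding, PROC FREQ's default of reporting the lowest level, and the template line being used without correction. The reach is confined to per-arm rates and intervals in the supportive multiple-imputation analysis. Nothing here bears on the primary estimate, its confidence interval or the comparison with the global study.

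**What to change.** In SAP 5.5.1.2.1, print the statement as `table response / binomial (level='1' cl=wilson correct);`.

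Copying the instruction from SAP 5.5.1.4.1 to sort 1 ahead of 0 would not be enough: if levels are ordered by value, sorting the data changes nothing unless `ORDER=DATA` is also set. Naming the level is the safer remedy.

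SAP Amendment 2 includes changes timed before the Week 52 database lock, so Week 16 tables may already exist. Any that show per-arm multiple-imputation rates should be checked against the non-responder-imputation rates and rerun if they are complements.

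The cost is one option in one line of code and a short check of existing output. No analysis or estimand changes.

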5.5.1.4 Analysis of binary and categorical data

5.5.1.4.1 Summary statistics for binary and categorical data

Summary statistics for discrete variables will be presented in contingency tables and will include count and frequency in each category. If applicable, confidence intervals will be derived as well based on the score method including continuity correction ([Newcombe 1998](#)):

With z as $(1-\alpha/2)$ -quantile of the standard normal distribution (SAS: $z=\text{probit}(1-\alpha/2)$), n as total number of subjects (i.e. number of subjects in the denominator), p as estimated crude incidence (number of subjects with event / n) and $q=1-p$)

Then the lower limit is

$$L = 100 \times \max \left(0, \frac{2np + z^2 - 1 - z \sqrt{z^2 - 2 - \frac{1}{n} + 4p(nq + 1)}}{2(n + z^2)} \right)$$

And the upper limit is

$$U = 100 \times \min \left(0, \frac{2np + z^2 + 1 + z \sqrt{z^2 + 2 - \frac{1}{n} + 4p(nq - 1)}}{2(n + z^2)} \right)$$

In addition, if $L > p$ then $L = p$ and if $U < p$ then $U = p$.

The placebo-adjusted response rates include 95% confidence interval will be derived using PROC FREQ with RISKDIFF statement. Note the response value should be sorted with '1' ahead of '0'. Fisher's exact test will be applied to rate events, pairwise treatment group comparisons to placebo to active controls (using PROC PREQ with FISHER statement). If appropriate, an exact $100*(1-\alpha)\%$ confidence interval (Clopper-Pearson 1934) will be obtained by using the SAS procedure PROC FREQ with the EXACT BINOMIAL statement. However, the confidence interval derived via the score method including continuity correction will be the default in safety analysis.

5.5.1.4.2 Logistic regression

Certain binary outcome variables, e.g. response outcomes, will be evaluated using a logistic regression model. The model will include factors and covariates as specified for respective analysis same as section 5.5.1.1.

5.5.1.5 Analysis of continuous data

5.5.1.5.1 Summary statistics for continuous data

Summary statistics (including N, mean, standard deviation, minimum, lower quartile, median, upper quartile, maximum) will be provided for continuous data by visit and treatment group.

5.5.1.5.2 Analysis of covariance

An analysis of covariance (ANCOVA) model will be used to analyze some endpoints. The model will include factors and covariates as specified for respective analysis. The SAS code below outlines a template for the analysis where covariates can be added or removed as required:

```
ods output diff=lsmeans=lsmeans;
proc mixed data=;
```

```
by visit;  
class treatment strata;  
model outcome = treatment strata baseline_weight;  
lsmeans treatment /diff cl;  
run;
```

Least-square-mean (LSM) estimated for each treatment group and LSM difference, confidence intervals and p-value for the difference between each dose of secukinumab and placebo, and between secukinumab doses if relevant, can be obtained.

5.5.1.5.3 Mixed-effects repeated measures model

Some endpoints will be analyzed using a longitudinal model that comprises several visits. The model used will be mixed model repeated measures (MMRM) with factors, covariates, interactions and covariance structure as specified for respective analysis. The SAS code below outlines a template for the analysis where covariates and interaction terms can be added or removed as required:

```
ods output diff=lsm_diff lsmeans=lsm_est;  
proc mixed data=;  
class treatment strata visit;  
model outcome=treatment strata visit baseline weight treatment * visit  
baseline * visit / ddfm=kr;  
repeated visit / type=un subject=;  
lsmeans treatment * visit / diff cl;  
run;
```

Least-square-mean (LSM) estimated for each treatment group and LSM difference, confidence intervals and p-value for the difference between each dose of secukinumab and placebo, and between secukinumab doses if relevant, can be obtained.

In case the MMRM model does not converge the following sequential steps will be used:

1. Change to ddfm=bw. If still no convergence, perform step 2.
2. Change to type=cs. If still no convergence, perform step 3.
3. Remove covariates in the following order until convergence: *weight, baseline*visit, strata*

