1.1 Study design

This is a randomized, double-blind, placebo-controlled study of secukinumab 150 mg s.c. to evaluate the safety, tolerability, and efficacy in Chinese participants with active non-radiographic axial spondyloarthritis (nr-axSpA).

A screening period of up to 10 weeks before randomization will assess participant eligibility, followed by 16 weeks of double-blind treatment period and 44 weeks open label period.

Approximately 134 participants will be randomized in a ratio of 1:1 to receive secukinumab 150 mg s.c. or placebo:

- Group 1: secukinumab 150 mg (1mL, 150 mg/mL) s.c. pre-filled syringe (PFS) at baseline (BSL), Weeks 1, 2, and 3, followed by administration every four weeks starting at Week 4
- Group 2: placebo (1 mL) s.c. PFS at BSL, Week 1, 2 and 3, followed by administration every four weeks starting at Week 4

Participants will be stratified at randomization according to the subgroup of objective sign of inflammation they belong to (based on their CRP and MRI status at screening: CRP+ and MRI+, CRP+ and MRI-, CRP- and MRI+).

Additionally, it is planned to enroll no more than approximately 10% Tumor Necrosis Factor – Inadequate Response (TNF α -IR) participants in the study.

The primary analysis will be performed after all participants complete Week 16 visit to support registration in China.

From Week 16, all participants will switch to open label secukinumab 150 mg s.c., including all placebo participants. The first dose of open label secukinumab 150 mg s.c. should start at the Week 16 visit, only after performing all assessments for that visit. However, all participants and investigators/site staff will remain blinded to the original randomized treatment group assignment (150 mg vs placebo).

At Week 24, non-responders (defined as not achieving ASAS20) will be escalated to secukinumab 300 mg s.c. Responders will continue secukinumab 150 mg s.c. treatment.

Study treatment will continue up to Week 48.

At end of treatment visit will be performed 4 weeks after last study treatment administration i.e. at Week 52 and a post treatment follow-up visit is to be done 12 weeks after last study treatment administration for all participants (regardless of whether they complete the entire study as planned or exit the study early).

A primary endpoint analysis will be conducted after all participants complete Week 16 visit. The final analysis will be conducted on all participant data at the time the study ends.

[figure not shown]

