2.1 Data analysis general information

The primary endpoint analysis will be performed after all participants complete Week 16 or discontinued earlier and the final analysis will be conducted on all participant data at the time the study ends, both by Novartis. Any data analysis carried out independently by the investigator should be submitted to Novartis before publication or presentation.

Novartis will perform the analysis at Week 16 and final analysis. Statistical software SAS version 9.4 or later will be used.

Summary statistics for continuous variables will generally include the number of participants (N), minimum, lower quartile, mean, standard deviation (SD), median, upper quartile, and maximum. For binary or discrete variables, the absolute number of participants in each category and relative frequencies will be provided.

Unless otherwise specified, two-sided 95% confidence intervals will be displayed.

In case of a global health disruptive event, such as pandemic/epidemic (e.g., COVID-19), affecting the ability of the patient or the site to adhere to protocol requirements and assessments and therefore leading to a potential increase in the number of missing measurements, additional analysis populations may be defined as per the instructions and procedures outlined in Section 16.9 in the protocol.

The efficacy evaluation of secukinumab relative to placebo will generally focus on the first 16 weeks of treatment unless otherwise specified.

Data analysis will be presented by treatment group. Efficacy and safety data for the 16-week placebo-controlled period and the entire treatment period as appropriate will be presented by the following two treatment groups. Participants may be included in more than one treatment group for some analysis (e.g. exposure adjusted adverse events over the entire treatment period).

These treatment groups represent the regimens to which participants will be eligible to be randomized:

- Secukinumab 150 mg regimen
- Placebo regimen

Note that the treatment groups above for a participant may differ depending on the time period of the analysis and whether one assesses the participant for efficacy or safety.

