2.6.2 Statistical hypothesis, model, and method of analysis

ASAS40 at Week 16

The proportion of patients meeting the response criteria will be evaluated using a logistic regression model with treatment group and stratification factor (CRP+/MRI+, CRP+/MRI-, CRP-/MRI+) as factors and weight as a covariate.

ASAS 5/6 at Week 16

The proportion of participants meeting the response criteria will be evaluated using a logistic regression model with treatment group and stratification factor (CRP+/MRI+, CRP+/MRI-, CRP-/MRI+) as factors and weight as a covariate.

BASDAI at Week 16

Between-treatment differences in the change from baseline in BASDAI will be evaluated using MMRM with treatment group, stratification factor (CRP+/MRI+, CRP+/MRI-, CRP-/MRI+) and analysis visit as factors and baseline BASDAI score and weight as continuous covariates. Treatment by analysis visit and baseline BASDAI score by analysis visit will be included as interaction terms in the model. An unstructured covariance structure will be assumed for the model.

BASDAI50 at Week 16

The proportion of participants meeting the response criteria at Week 16 will be evaluated using a logistic regression model with treatment group and stratification factor (CRP+/MRI+, CRP+/MRI-, CRP-/MRI+) as factors and baseline weight and baseline BASDAI score as covariates.

hsCRP at Week 16

For the change in hsCRP, since evidence from the literature would suggest that the data are not normally distributed (Huffman et al. 2006), analysis will be performed on the \log_e ratio of the treatment value vs baseline value (calculated by dividing the post-baseline value by the baseline value and then applying the \log_e transformation) to normalize the distribution of hsCRP at each analysis visit. Between-treatment differences in the change in hsCRP relative to baseline will be evaluated using MMRM with treatment group, stratification factor (CRP+/MRI+, CRP+/MRI-, CRP-/MRI+) and analysis visit as factors and \log_e baseline hsCRP and weight as continuous covariates. Treatment by analysis visit and \log_e baseline hsCRP by analysis visit will be included as interaction terms in the model. An unstructured covariance structure will be assumed for the model. The estimate and the 2-sided 95% confidence intervals obtained from the model will be back transformed to the original scale.

BASFI at Week 16

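### If the unstructured MMRM fails to converge, the SAP's fallback to compound symmetry gives Week 16 intervals the wrong width whenever variances differ between visits

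*SAP*

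**What the plan says.** SAP Section 2.6.2 analyses change in BASDAI, hsCRP (log ratio), BASFI, SF-36 PCS and ASQoL by MMRM. For each it states: "An unstructured covariance structure will be assumed for the model". The code template in SAP Section 5.5.1.5.3 agrees ("repeated visit / type=un subject") and uses the Kenward-Roger method ("baseline * visit / ddfm=kr"). It has no EMPIRICAL option, so the standard errors are model-based.

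The same section gives three steps for non-convergence. The first touches only the degrees of freedom: "Change to ddfm=bw. If still no convergence, perform step 2". After that, the covariance structure itself is replaced: "Change to type=cs. If still no convergence, perform step 3". The last resort is a simpler mean model: "Remove covariates in the following order until convergence". There the SAP gives up body weight first, next the interaction of baseline with visit, and finally the stratification factor.

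No step adds a robust standard error, and step 3 leaves compound symmetry in place. On reporting, SAP Section 2.1 says: "Unless otherwise specified, two-sided 95% confidence intervals will be displayed".

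**The concern.** Step 1 alters how degrees of freedom are computed. The likelihood being maximised and the unstructured matrix stay the same, so a covariance fit that fails before step 1 fails after it. In practice the rule therefore goes from a structure with a separate variance for every visit to one with a single variance for all of them, with nothing in between.

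Compound symmetry has two parameters and will nearly always converge, so it would usually be the final model. Week 16 is the only visit named in the secondary objectives. If its variance differs from the average over visits, the reported interval has the wrong width. SAP Section 3.1 describes the study as one of estimation rather than hypothesis testing, so for these endpoints the interval is the main statement of uncertainty.

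**Working it through.** The documents state no operating figure for the MMRM or its fallback. Their only design figures concern ASAS40 (77.3% and 90.7%). Exact binomial enumeration with 60 per arm reproduces them (0.7730 and 0.9072), but they have no bearing here.

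**Inputs from the documents**
- About 134 participants, 1:1, so 67 per arm (SAP Section 1.1).
- BASDAI, BASFI and hsCRP are in Group 1 of SAP Table 2-1. Up to Week 16 they have seven post-baseline visits: Weeks 1, 2, 3, 4, 8, 12 and 16.
- ASQoL and SF-36 are in Group 3. Up to Week 16 they have two: Weeks 8 and 16.
- Two-sided 95% intervals.

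**Assumed, because the documents give nothing:** the SD at each visit, the correlation between visits and the dropout rate.

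**Formula.** With complete data, the compound-symmetry standard error at any visit rests on the variance averaged over visits. At Week 16:

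SE ratio = √(mean of SD² over visits) / SD at Week 16; coverage = 2Φ(1.96 × ratio) − 1.

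**Worked case: SD grows 50% from Week 1 to Week 16, linearly by week.** The SDs are 1, 1.033, 1.067, 1.1, 1.233, 1.367 and 1.5. The mean square is 10.054 / 7 = 1.436. The ratio is √1.436 / 1.5 = 0.799, and coverage is 2Φ(1.566) − 1 = 88.3%.

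**Range for seven visits**

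| SD at Week 16 / SD at Week 1 | SE ratio, growth by visit number | Coverage | SE ratio, growth by week | Coverage |
|---|---|---|---|---|
| 0.8 | 1.128 | 97.3% | 1.160 | 97.7% |
| 1.0 | 1.000 | 95.0% | 1.000 | 95.0% |
| 1.25 | 0.902 | 92.3% | 0.877 | 91.4% |
| 1.5 | 0.841 | 90.1% | 0.799 | 88.3% |
| 2.0 | 0.768 | 86.8% | 0.708 | 83.5% |

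**Two visits (SF-36 PCS, ASQoL).** Take the same 50% growth from Week 1 to Week 16.
- Growth by week: SD 1.233 at Week 8 and 1.5 at Week 16. Ratio √((1.521 + 2.25)/2) / 1.5 = 0.915.
- Growth by visit number: SD 1.333 at Week 8. Ratio √((1.778 + 2.25)/2) / 1.5 = 0.946.

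The standard error is about 5% to 8% too small, and coverage is about 93% to 94%.

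**Simulation.** N = 134, seven visits, the SAP's fixed effects, SD changing by week, and 1,500 trials per scenario. Correlation was exchangeable (0.6) or autoregressive (0.85), with 0% or 10% dropout.
- Compound symmetry, model-based: 94.9% and 96.1% with equal variances, 90.9% at 25% growth, 86.2% to 87.4% at 50%, and 81.3% to 82.5% at 100%. The Monte Carlo standard error near 87% is √(0.87 × 0.13 / 1500) = 0.9 points. The 50% results lie slightly below the formula.
- Same fits with sandwich standard errors, all growing-variance scenarios: 93.5% to 94.4%.
- Week 16 ANCOVA, a reference that uses only the Week 16 variance: 94.3% to 94.9%.

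**The case against.** The fallback is pre-specified and sequential, so it leaves no room for choosing a model after seeing results, and which structures stand between unstructured and compound symmetry is partly a matter of taste. It applies only if the unstructured fit fails, and failure is not shown to be likely: with seven visits the matrix has 7 × 8 / 2 = 28 parameters for about 134 participants. The primary ASAS40 analysis is logistic, and SI joint edema uses ANCOVA after multiple imputation, so neither is affected. All of this stands and keeps the point small. It does not make the rule sound where the rule is used.

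Three stronger readings are tempting, and the documents do not support them.

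- A reader might infer that the Week 16 intervals would be too narrow. That needs a Week 16 variance above the average over visits. The relevant variance is residual, after baseline and its interaction with visit, and for hsCRP it is on the log-ratio scale. The documents give no visit-specific SDs, so the direction is open.
- A reader might apply the seven-visit figures to all five endpoints. With two visits, the unstructured matrix has three parameters and is unlikely to fail. Heterogeneous Toeplitz and heterogeneous compound symmetry are then the same model as unstructured, so a longer ladder adds nothing there.
- A reader might count all 16 post-baseline Group 1 visits in Table 2-1, giving 16 × 17 / 2 = 136 parameters, and conclude that failure is likely. SAP Section 2.1 focuses the comparison with placebo on the first 16 weeks, and Section 2.1.1.1 presents placebo-controlled efficacy data at the primary endpoint analysis. The 136-parameter model is speculation.

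**Conclusion.** The point holds as a minor weakness in a contingency rule. If the unstructured model fails, the Week 16 interval comes from a model with one variance for all visits and no robust correction. Its width is right only if the Week 16 variance equals the average over visits.

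For BASDAI, BASFI and hsCRP, assumed SD growth of 25% to 50% from Week 1 to Week 16 makes the standard error about 10% to 20% too small, with coverage of about 88% to 92% by the formula. A fall of 20% makes it 13% to 16% too large, with coverage above 97%. Equal variances give no error. For SF-36 PCS and ASQoL the effect is smaller and the trigger remote.

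The mechanism is algebra. The sizes rest on the assumed SD patterns and, in the formula, on complete data. How likely the fallback is cannot be judged from the documents.

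**What to change.** In SAP Section 5.5.1.5.3:

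- Between unstructured and `type=cs`, try heterogeneous-variance structures, for example heterogeneous Toeplitz (7 variances + 6 correlations = 13 parameters for seven visits), then heterogeneous compound symmetry (7 + 1 = 8).
- For any structure other than unstructured, use EMPIRICAL (sandwich) standard errors with `ddfm=bw`. The pairing matters, because SAS does not combine EMPIRICAL with the template's `ddfm=kr`. A small-sample correction is preferable, since plain sandwich intervals covered about 94% in the simulation.

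Heterogeneous Toeplitz indexes correlation by visit lag, so it treats Weeks 3 to 4 like Weeks 12 to 16 although the spacing differs. The sandwich standard error guards the interval against that. It does not correct the estimate: with data missing at random, the Week 16 estimate still depends on the assumed covariance, which is why the richer structures should come first.

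The cost is a few lines of SAP text and code and slightly more programming. Nothing changes if the unstructured model converges. If Week 16 results already exist, state which structure each endpoint used and rerun any that ended in compound symmetry.
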